## 8.7 MEDICAL HISTORY

The percentage of subjects with abnormal medical history findings will be summarized by body system, by treatment arm, for the mITT population.

## 8.8 PRIOR AND CONCOMITANT MEDICATIONS

Prior medications are those that were used before the start of the trial (within 10 weeks prior to Day 0). Concomitant medications are those used during the course of the trial (on or after Day 0). Partial start dates of prior and concomitant medications will be assumed to be the earliest possible date consistent with the partial date. Partial stop dates of prior and concomitant medications will be assumed to be the latest possible date consistent with the partial date. Data for all prior and concomitant medications will be summarized with percentages by treatment arm, for the mITT population.

## 8.9 EFFICACY ANALYSIS

The true treatment effect on the primary endpoint is  $p$ , where  $p$  denotes the true population probability of the primary endpoint for each arm. The primary hypothesis of superiority is:  $H_0: p \leq 0.02$  vs.  $H_1: p > 0.02$ , for each treatment arm separately.

A p-value for these hypothesis tests and corresponding 95% confidence intervals will be computed based on the method of Clopper-Pearson. Superiority will be concluded if the one-sided p-value is  $< 0.025$  and the corresponding lower bound of the 95% CI exceeds 0.02.

The secondary efficacy binary endpoints will be analyzed in the same manner as the primary hypothesis, but without the hypothesis test p-values.

For the analyses, the efficacy time frame is defined by any time starting from 14 days prior to the -specified visit week.

The anatomic extent endpoint will be analyzed by calculating the mean percent change and associated 95% t-distribution based confidence interval. The percentage of subjects with no clinically significant lesion resolution (reduction in lesion size of 25% or less), partial lesion resolution (26-99% reduction), and complete reduction (100% reduction) will be summarized with point estimates and associated Clopper-Pearson 95% confidence intervals.

An exploratory analysis will examine clearance outside of the vulva. This will be analyzed in the same manner as vulvar clearance.

An exploratory analysis will examine the relationship between the primary efficacy endpoint and HLA results. As these results are categorical, relationships will be examined with contingency tables and logistic regression models which model the primary endpoint versus these results and treatment group as regressor variables.

An exploratory analysis will examine the relationship between the primary efficacy endpoint and needle depth into muscle. A logistic regression model which models the primary endpoint versus these results and treatment group as regressor variables will be used.

## 8.10 IMMUNOGENICITY ANALYSIS

Post-baseline cellular and humoral response magnitude will be summarized with medians and associated non-parametric 95% CIs. Post-baseline tissue response magnitude will be summarized with means and associated t-distribution based 95% CIs.

Valid samples for statistical analysis purposes will be those collected within 7 or 14 days of the specified time points (see [Table 1](#)). Baseline is defined as the last measurement prior to the first treatment administration.

## 8.11 SAFETY ANALYSES

### 8.11.1 ADVERSE EVENTS

All AEs will be summarized among the safety population by frequency per treatment arm. These frequencies will be presented overall and separately by dose, and will depict

overall, by system organ class and by preferred term, the percentage of subjects affected. Additional frequencies will be presented with respect to maximum severity and to strongest relationship to Study Treatment. Multiple occurrences of the same AE will be counted only once following a worst-case approach with respect to severity and relationship to Study Treatment. All serious AEs will also be summarized as above.

The main summary of safety data will be based on events occurring within 14 days of any dose. For this summary, the frequency of preferred term events will be summarized with percentages and 95% Clopper-Pearson confidence intervals. Separate summaries will be based on events occurring within 7 days of any dose and regardless of when they occurred.

Any AEs with a missing or partial onset date will be included in the overall AEs, but not be included within specified day-range summaries. AE duration will be calculated as (Stop Date – Start Date) + 1.

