### 7.3.1 ADVERSE EVENTS OF SPECIAL INTEREST

Adverse events of special interest (AESI) are the adverse events deemed related to VGX-3100 delivered with CELLECTRA® 2000 that require expedited communication from the site to the Sponsor and meet any of the following criteria:

- Grade 3 or greater persistent administration site erythema, and/or induration recorded  $\geq 2$  hours immediately after Study Treatment
- Grade 4 or greater persistent administration site pain, tenderness recorded  $\geq 2$  hours immediately after Study Treatment
- Grade 3 or greater fever
- Grade 3 or greater systemic symptoms, including generalized pruritus
- Grade 3 or greater laboratory abnormalities

As per the Toxicity Grade for Healthy Adults. The most severe grade for that particular event is to be documented in the CRFs.

Sites will inform the Sponsor of an AESI within 24 hours via method described in [Section 7.4.2](#), to discuss whether further dosing should continue.

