#### 8.11.2 LABORATORY DATA

Continuous response variables per time point and changes from baseline will be summarized with mean, median, minimum, and maximum values, and categorical response variables will be summarized per time point with percentages, by treatment arm. Baseline is defined as the last measurement prior to the first treatment administration.

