#### 8.11.3 VITAL SIGNS

Measurements for vital signs as well as changes from baseline will be summarized with descriptive statistics: mean standard deviation, minimum, median, and maximum values by time point and treatment arm, for the mITT population. Baseline is defined as the last measurement prior to the first treatment administration.

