#### 6.3.3.6 LABORATORY EVALUATIONS

At screening, blood samples will be taken to be tested for serum chemistry and hematology.

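### The main adverse-event table is tied to 14 days after an undefined dose, which does not match imiquimod exposure; vital signs sit on the efficacy set, and planned laboratory changes have no post-baseline draws

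*Protocol*

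**What the plan says.** **Adverse events (section 8.11.1).** The section opens broadly: "All AEs will be summarized among the safety population by frequency per treatment arm". It then names the main table: "The main summary of safety data will be based on events occurring within 14 days of any dose". Preferred-term percentages with Clopper-Pearson 95% intervals are specified for that table only. Two further tables follow: "Separate summaries will be based on events occurring within 7 days of any dose and regardless of when they occurred". On incomplete dates: "Any AEs with a missing or partial onset date will be included in the overall AEs, but not be included within specified day-range summaries".

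**Vital signs and examinations (8.11.3, 8.11.4).** Vital signs are summarised "by time point and treatment arm, for the mITT population", and physical examinations use the same population. Section 8.4 defines mITT as the primary efficacy population: dosed subjects who have the endpoint being analysed, grouped as randomised. It also defines a safety set of everyone dosed, analysed as treated.

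**Laboratory data.** Section 8.11.2: "Continuous response variables per time point and changes from baseline will be summarized". Section 7.3 lists changes in hematology, chemistry and urinalysis among the safety assessments, and section 7.3.1 includes "Grade 3 or greater laboratory abnormalities" among the events of special interest. On collection, section 6.3.3.6 says: "At screening, blood samples will be taken to be tested for serum chemistry and hematology". Table 1 and section 6.5 also place these tests at screening only.

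**Versions.** Section 8.11 is quoted from Version 1.1; Version 1.0 reads the same. The Version 1.2 text at hand stops at section 6.12, so its section 8.11 could not be read. Its list of changes names only the removal of one patient-reported outcome instrument and calls the rest administrative.

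**The concern.** Safety of VGX-3100 alone or with imiquimod is the first secondary objective, so the main safety table is the one readers will use to set the arms side by side. The arms differ only in imiquimod, which is applied three times a week for 20 weeks. The main table is built around separate short windows that suit an injection. It should suit both products, or at least say which product opens a window. The protocol does not define *any dose*, and Table 5 gives a dose for each product.

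The partial-date rule bears on the same table. Injection reactions have a dated 7-day diary (6.3.3.9). Imiquimod reactions do not: the dosing log records application dates, and subjects contact the site to report events (6.3.3.10). Incomplete onset dates may therefore be commoner for imiquimod reactions, but that is an inference; no document gives a rate.

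The other two points concern both arms. An efficacy population is used for safety measurements although a safety set exists, and an analysis is promised for data that the schedule does not collect.

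**Working it through.** The protocol gives no figure here to reproduce. The check counts days and compares passages.

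**Inputs.** VGX-3100 on Day 0 and at Weeks 4, 12 and 24, that is Days 0, 28, 84 and 168, with optional doses at Weeks 52 and 78 (synopsis). Imiquimod for 20 weeks = 140 days, 3 × 20 = 60 applications (3.1). Study length Day 0 to Week 100 = 701 days. Evaluable at Week 48: 90% (8.3). Arms of 24 and 12.

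**Reading 1: a dose is a VGX-3100 dose.**
- The windows after Days 0, 28 and 84 fall inside the imiquimod period. The window after Day 168 opens after imiquimod has ended.
- Dose day plus 14 further days: 3 × 15 = 45; 45/140 = 32%.
- Dose day counted as the first of 14: 3 × 14 = 42; 42/140 = 30%.
- Applications on a Monday/Wednesday/Friday pattern from Day 0: 7 per window, 3 × 7 = 21 of 60 (35%).
- Moving doses 2 and 3 by up to 7 days leaves the count at 45.
- Whole study: 4 × 15 = 60 of 701 days (9%) with four doses; 6 × 15 = 90 of 701 (13%) with six.
- The 7-day table: 3 × 8 = 24 of 140 imiquimod days (17%).

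**Reading 2: imiquimod applications also count.**
- On the same pattern the last application is Day 7 × 19 + 4 = 137, and its window ends on Day 151. The combination arm is covered without a gap from Day 0 to Day 151, which is 152 days, or about 20 + 2 = 22 weeks. All 140 imiquimod days are included.
- Adding the 15 days from Day 168 gives 152 + 15 = 167 days, against 60 in the VGX-3100-alone arm. The same background event rate would then yield more counted events in the combination arm through longer observation alone.

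Reading 1 is the likelier one, because 8.11.1 also tabulates events by dose, which makes little sense for 60 applications. The text does not settle it.

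**mITT for vital signs.** If the required endpoint is the Week 48 result, 0.90 × 24 = 21.6 and 0.90 × 12 = 10.8 women remain. That is 32.4 of 36, so about 3 to 4 dosed women would be left out. If the endpoint is read per analysis, almost nobody is lost, but grouping is still as randomised.

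**Laboratory passages side by side.** Planned: values per time point and change from baseline (8.11.2), changes as a safety assessment (7.3), and a Grade 3 criterion (7.3.1) that feeds the one-third pausing rule (7.3.2). Scheduled safety draws after baseline: 0. Change from baseline cannot be computed for anyone from scheduled data.

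**The case against.** The strongest reply is that nothing is lost. Section 8.11.1 summarises all AEs in the safety population by arm, system organ class, preferred term, severity and relationship. It does the same for serious AEs and adds a table without a time limit. AEs are collected from consent to Week 100 (7.2). Partial-date events leave only the day-range tables. This stands. It rules out a reading that a reader might infer, namely that AEs are dropped from the analysis or that the safety of the combination arm is understated overall.

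The 30-32% is also a share of days, not of events or subjects. A woman is counted once per event, so a reaction that starts in the first two weeks is in the main table. The protocol's Table 10 shows erythema in 74 of 114 (65%) and erosion in 35 of 114 (31%) of women using imiquimod for genital warts, but gives no onset times. It shows that such reactions are expected, not how many fall outside the windows. This also stands.

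The mITT wording, the laboratory schedule and the partial-date rule apply to both arms in the same way and do not show bias against either. Clinically prompted laboratory abnormalities can still be recorded as AEs (7.1.9), so the special-interest criterion is not empty; it only lacks scheduled data. Handling of incomplete dates is often left to an analysis plan, but here the protocol states a rule, and that rule governs the main table.

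None of this answers the narrower point: the one table given prominence and intervals has a window that either misses most imiquimod days or differs between the arms.

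**Conclusion.** The concern holds for the main AE table. On the VGX-3100 reading, that table leaves about 68-70% of imiquimod days outside its windows; on the other reading, it observes one arm for 167 days and the other for 60 through the fourth dose. Either way it is a poor basis for a between-arm safety comparison. These figures assume the nominal schedule and a Monday/Wednesday/Friday pattern. How many subjects' events are affected cannot be derived from the protocol.

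Using mITT for vital signs and examinations is a misassignment: at most about 3 to 4 of 36 women lost on the strict reading, and as-randomised grouping on either reading. The laboratory passages contradict the schedule outright. Neither point is specific to an arm. A reader might combine all of these into a claim that combination-arm safety is understated; the summary of all events regardless of timing prevents that conclusion. The primary efficacy analysis is not touched. The changes should be made, but the trial's conclusions do not depend on them.

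**What to change.** - **Main AE table.** Give the Clopper-Pearson intervals to a table that uses the same period in both arms and covers the imiquimod period and every VGX-3100 dose, including optional doses 5 and 6. The already planned summary of events regardless of timing would serve. A cut-off soon after dose 4 would not, because it loses events after Weeks 52 and 78.
- **Supporting tables.** Keep the 7- and 14-day tables, and state that their windows run from VGX-3100 doses.
- **Partial dates.** Count an AE with a partial onset date inside a day-range window unless the known parts of the date exclude it. Section 8.8 already has date rules for medications.
- **Population.** Summarise vital signs and physical examinations on the as-treated safety set.
- **Laboratory passages.** Reconcile sections 7.3, 7.3.1 and 8.11.2 with Table 1 and sections 6.3.3.6 and 6.5. Which of them should give way is a clinical decision for the sponsor.

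The first four changes cost wording and table shells. AE percentages in the main table can only stay or rise on the VGX-3100 reading, probably slightly, and a longer period admits more background events; the short-window tables remain for acute reactions. The laboratory reconciliation needs a sponsor decision and perhaps an amendment.

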#### 8.11.2 LABORATORY DATA

Continuous response variables per time point and changes from baseline will be summarized with mean, median, minimum, and maximum values, and categorical response variables will be summarized per time point with percentages, by treatment arm. Baseline is defined as the last measurement prior to the first treatment administration.

#### 8.11.3 VITAL SIGNS

Measurements for vital signs as well as changes from baseline will be summarized with descriptive statistics: mean standard deviation, minimum, median, and maximum values by time point and treatment arm, for the mITT population. Baseline is defined as the last measurement prior to the first treatment administration.

#### 8.11.4 PHYSICAL EXAMINATION

The percentage of subjects with abnormal physical examination findings at each time point will be summarized by treatment arm and by body system, for the mITT population.

#### 8.11.5 PATIENT REPORTED OUTCOMES

As an exploratory endpoint, patient reported outcomes will be summarized with medians or proportions of subjects with endpoints and associated non-parametric or Clopper-Pearson 95% CIs, for continuous responses and binary responses, respectively.

#### 8.11.6 MISSING VALUES

Missing data will not be imputed or replaced, and calculations will be done on reported values.

#### 8.11.7 INTERIM ANALYSIS

No formal interim analyses will be performed for this study.

## **9. ETHICS**

### **9.1 INVESTIGATOR AND SPONSOR RESPONSIBILITIES**

The investigator and Sponsor are responsible for ensuring that the clinical study is performed in accordance with the protocol, the Declaration of Helsinki, principles of Good Clinical Practice (GCP), and applicable regulatory requirements.

### **9.2 INSTITUTIONAL REVIEW BOARD OR ETHICS COMMITTEE (IRB/EC)**

The investigator will undertake the study after full approval of the protocol and adjunctive materials (e.g., informed consent form, advertising) has been obtained from the applicable IRB/EC and a copy of this approval has been received by the sponsor.

Investigator responsibilities relevant to the IRB include the following:

- During the conduct of the study, submit progress reports to the IRB/EC as required.
- Notify the Sponsor immediately of any SAEs or serious unanticipated adverse device effects.
- If Sponsor notifies you about any reportable safety events notify the IRB immediately.
- As required, obtain approval from the IRB/EC for protocol amendments and for revisions to the consent form or subject recruitment advertisements;
- Reports on, and reviews of, the trial and its progress will be submitted to the IRB by the investigator at intervals stipulated in their guidelines and in accordance with pertinent regulations and guidelines.
- Maintain a file of study-related information that includes all correspondence with the IRB;
- Notify IRB when study is completed (i.e. after the last study visit of the final study subject);
- After study completion provide the IRB with a final report on the study.

### **9.3 OFFICE OF BIOTECHNOLOGY ACTIVITIES (OBA)**

The investigator and Sponsor are responsible for ensuring that the clinical study is reviewed and approved according to local and applicable global regulations (e.g., NIH Office of Biotechnology Activities) governing research that involves recombinant or synthetic nucleic acid molecules.

### **9.4 COMPLIANCE WITH INFORMED CONSENT REGULATIONS**

Written informed consent is to be obtained from each subject prior to Screening into the study, and/or from the subject's legally authorized representative. The process for obtaining informed consent must also be documented in the subject's medical record.

## **9.5 COMPLIANCE WITH IRB/EC REQUIREMENTS**

This study is to be conducted in accordance with applicable IRB/EC regulations. The Investigator must obtain approval from a properly constituted IRB/EC prior to initiating the study and re-approval or review at least annually. Sponsor is to be notified immediately if the responsible IRB/EC has been disqualified or if proceedings leading to disqualification have begun. Copies of all IRB/EC correspondence with the investigator must be provided to Sponsor.

## **9.6 COMPLIANCE WITH GOOD CLINICAL PRACTICE**

This protocol is to be conducted in accordance with the applicable GCP regulations and guidelines.

## **9.7 COMPLIANCE WITH ELECTRONIC RECORDS/SIGNATURES REGULATIONS (21CFR PART 11)**

When applicable, this study is to be conducted in compliance with the regulations on electronic records and electronic signature.

## **9.8 COMPLIANCE WITH PROTOCOL**

Subjects will be asked to complete a participant diary and for subjects in the imiquimod arm a dosing log during their study participation. Subjects will be provided with Investigator emergency contact information and advised to report all adverse events. While every effort should be made to avoid protocol deviations, should a deviation be discovered, the Sponsor must be informed immediately. Any protocol deviation impacting Subject safety must be reported to the Medical Monitor immediately.

## **9.9 CHANGES TO THE PROTOCOL**

The Investigator should not implement any deviation from or changes to the protocol without approval by the Sponsor and prior review and documented approval/favorable opinion from the IRB of a protocol amendment, except where necessary to eliminate immediate hazards to study subjects, or when the changes involve only logistical or administrative aspects of the study (e.g., change in monitors, change of telephone numbers).

# **10. DATA COLLECTION, MONITORING AND REPORTING**

## **10.1 CONFIDENTIALITY AND PRIVACY**

A report of the results of this study may be published or sent to the appropriate health authorities in any country in which the study products are legally marketed or may ultimately be marketed, but the subject's name will not be disclosed in these documents. The subject's name may be disclosed to the study sponsor, Sponsor, the governing health authorities or the Food and Drug Administration (FDA), if they inspect the study records. Appropriate precautions will be taken to maintain confidentiality of medical records and personal information.

Written Authorization and other documentation in accordance with the relevant country and local privacy requirements (where applicable) are to be obtained from each subject prior to enrollment into the study, and/or from the subject's legally authorized representative in accordance with the applicable privacy requirements (e.g., the Health Insurance Portability and Accountability Act Standards for Privacy of Individually Identifiable Health Information (HIPAA)).

Information about study subjects will be kept confidential and managed according to the requirements of the Health Insurance Portability and Accountability Act of 1996 (HIPAA). Those regulations require a signed subject authorization informing the subject of the following:

- What protected health information (PHI) will be collected from subjects in this study
- Who will have access to that information and why
- Who will use or disclose that information
- The rights of the research subject to revoke their authorization for use of their PHI

The rights of the research subject to revoke their authorization for use of their PHI.

## 10.2 SOURCE DOCUMENTS

Source data is all information, original records or clinical findings, laboratory results, observations, or other activities in a clinical trial necessary for the reconstruction and evaluation of the trial. Source data are contained in original source documents. Examples of these original documents, and data records include: hospital records, clinical and office charts, laboratory notes, memoranda, subject's diaries or evaluation checklists, pharmacy dispensing records, recorded data from automated instruments, copies or transcriptions certified after verification as being accurate and complete, microfiches, photographic negatives, microfilm or magnetic media, x-rays, subject files, and records kept at the pharmacy, at the laboratories, and at medical records and within information technology systems that are involved in the clinical trial.

A medical history must be present in the source documents. A medication history must be present in the source documents. All prescription and nonprescription medications taken within 1 week prior to entry must be recorded on the CRF. Actual or estimated start and stop dates must be provided.

